H. Background and Significance (Describe succinctly and clearly the past findings which justify the plan for this project. A summary of the relevant literature in the area of interest and reports of previous studies should be included.): **¹Between two and three million American adults currently suffer from schizophrenia.² The modal onset occurs in early adulthood, and roughly two-thirds of affected individuals experience a chronic or fluctuating course of illness.³ This latter group is amongst the most expensive receiving psychiatric services, with the overall direct treatment costs and indirect costs incurred due to unemployment and lost productivity approaching \$63 billion in the United States.¹ Although antipsychotic medications have been readily available for more than half a century, the impact of these agents on functional outcomes has been modest, even when medication regimes have been optimized.⁴ By contrast, psychiatric rehabilitation programs have been shown to improve psychosocial functioning.⁵ Vocational rehabilitation services, in particular supported employment (SE), have the best evidence base. As compared to those patients not participating in such services, patients successfully engaged in SE are more likely to be working competitive jobs, working full time, earning higher wages, and reporting a higher quality of life.⁶ Furthermore, steady employment has been shown to generate significant savings in the use of mental health services use compared to patients who are minimally employed.⁷ Given the impressive benefits of SE programs, it is disappointing that so few eligible patients agree to participate in them. Patients who do not engage in treatment achieve the poorest outcomes,⁸ have the lowest quality of life, and are at risk for symptom exacerbation, recurring hospitalization, persistent homelessness, violence toward others, and suicide.⁹ Indeed, “providing appealing**

and effective treatment to those who could derive benefit but who choose to avoid treatment remains an ongoing challenge”⁹ in schizophrenia.

Our group has responded to this challenge by developing a new integrated Cognitive Behavior Therapy (iCBT) protocol designed for low functioning patients with schizophrenia who are not participating in psychiatric rehabilitation services such as SE. It is pragmatic, multimodal, recovery-oriented, and extends to some of the most challenging patients (e.g., those with the predominant negative symptoms and/or low insight). Our recent article in the *Archives of General Psychiatry* demonstrates that this approach is efficacious at improving functional outcomes and increasing motivation relative to standard treatment when delivered by PhD therapists in a university setting.¹⁰ The current proposal aims to compare usual care to iCBT to see if there are differences in their ability to improve work outcomes achieved by VA patients with schizophrenia enrolled in SE. Not being enrolled in SE or being enrolled but not active both produce little benefit. The goal of adding iCBT or usual care is to increase the patients’ motivation to achieve their own recovery goals and direct their own engagement in constructive activity such as utilization of SE.

- I. **Purpose of the Project** (Clearly provide the purpose of this research project.): **The objective of the current proposal is to improve work outcomes and functional outcomes of veterans with functional disability who are not participating in psychiatric rehabilitation services that are available to them.**
- J. **Describe the Research Questions or Hypotheses** (that is, what questions are you trying to address by conducting the research.): **The objective of the current proposal is to evaluate whether iCBT vs. treatment as usual can improve engagement and success in an existing SE program among the most functionally disabled patients with schizophrenia.**
- K. **Primary Outcome Variable(s)** (Define the primary outcome variable(s) used to support the study objectives (e.g. if the objective is to show that treatment A is superior to treatment B in the treatment of subjects with essential hypertension, the primary outcome variable is blood pressure measurement.): **Our primary specific aim is to determine whether iCBT will significantly improve work outcomes at post-treatment to a greater extent than usual care in low functioning patients with schizophrenia who are enrolled in SE. The primary outcome measures are several work-related indices of work participation across the 18 months of active study involvement, including the following: 1) instances of job attainment, 2) average days worked per week while employed, 3) average number of hours worked per week while employed, 3) total weeks worked , and 4) a composite of these indices.**
- L. **Secondary Outcome Variable(s)** (Define the secondary outcome variables. Such measured variables should also include the timing of measurement.): **The second trial outcome measures will include the Work behavior Inventory (WBI) and the Specific Levels of Functioning Scale (SLOF). A significant ITT difference on the WBI and the total SLOF score across 6 and 12 months would support the hypothesis that ICBT is more efficacious than usual care at improving functioning by the end of treatment (Secondary Aim 1). Similarly, WBI score and the SLOF total score at 18 months is a secondary outcome, and the separate ITT effects on functioning at 18 months with the respective month-treatment interaction in favor of iCBT would support the hypothesis that it promotes better functioning than usual care during the 6 months after the completion of treatment (Secondary Aim 3).**
- M. **Study Design and Methods:**
 1. Is this a clinical trial? YES NO (Randomized non-drug/non-medical device intervention)
 - 1.1. If yes, what type? Check all that apply.
 Phase I Phase II Phase III Phase IV
 - 1.2. If yes, this study must be registered on [Clinicaltrials.gov](https://clinicaltrials.gov).

2. Design

2.1. What research methods will be used in the project? Check all that apply.

 Surveys/Questionnaires	 Interviews	 Audio Taping
 Behavioral Observations	 Chart Reviews	 Video Taping
 Focus Groups	 Randomization	 Double-Blind
 Control Group	 Placebo	 Withhold/Delay Treatment
 Specimen Collection	 Deception	 Telephone Survey
 Other (Describe)		

2.2. Describe how randomization or other treatment assignment will be made.

Randomization will occur on a 1:1 basis to one of the two study conditions (iCBT or usual care) using a permuted block randomization with randomly varying block sizes of 2, 4 and 6 and stratification by gender (because females with schizophrenia have a better course and may respond better to traditional CBT). The study biostatistician will generate randomization lists based on the above procedure. The encrypted randomization file will be located on a server (i.e., \\VHAPHIFPCMIRECC\Research Studies\[name] -Integrated CBT to Improve Work) that is not accessible to the study personnel who make subject contact during the randomization procedure. S/He will access the file and provide the randomization token. S/He will not have subject contact nor know which condition is being assigned. Further, s/he does not have a stake in the outcome of the study.

2.3. For retrospective research studies, provide the "look-back" period. (e.g., December 1, 1999 through December 31, 2008.) **Not Applicable.**

3. Study Duration

3.1. Provide the estimated length of time to enroll all subjects and complete the study. **To allow that not all identified patients will qualify and not all qualifying patients will elect to participate, we will conduct more baseline screenings than required. We propose, accordingly, to consent to the baseline assessment 48 patients in the first year of the study (months 6 to 12), 96 patients in the second year (months 13 to 24), and 48 patients in the third year (months 25 to 30), producing 24 randomized patients in year 1, 48 in year 2, and 24 in year 3, for an estimated total of 96 randomized subjects (48 per group). All 96 subjects will be randomized by middle of the third year. Data collection will be complete after the middle of the fourth year.**

3.2. Explain the expected duration of subject participation including any follow-up. **iCBT will be delivered as a group therapy for 12 months of weekly or biweekly sessions (see below). Usual care (and iCBT) will entail continued access to all treatments available to all Veterans receiving treatment at the CMC VAMC Mental Health Clinical without restriction. Blind, reliable independent assessors, who are part of the study team, will reassess participants every 6 months after participants begin treatment over an 18-month participation period, producing mid-treatment (6 month) end-of-treatment (12 month), and post-treatment (18 month) assessments.**

3.3. Specify the projected date of completion of the proposed study. **We plan to complete the study at the end of fiscal year 2018.**

4. Drug Information (If not applicable state, "Not Applicable.") **Not Applicable.**

4.1. Specify if the drug or biological agent is:

- 4.1.1. FDA approved
- 4.1.2. Used for off-label purposes
- 4.1.3. Not yet FDA approved.

4.2. Include the FDA Investigational New Drug (IND) number for all non-FDA approved and off-label drugs, biological agents or nutritional supplements. If not applicable state, "Not Applicable."

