Eligible subjects who give a second informed consent will be randomly assigned to receive either iCBT or to usual care. All randomized participants will enter into supportive employment at the CMCVAMC. iCBT will be delivered as a group therapy for 12 months of weekly or biweekly sessions (see below). iCBT sessions will take approximately 1 hour. Blind, reliable independent assessors will reassess participants every 6 months after participants begin treatment groups over an 18-month participation period, producing mid-treatment (6 month) end-of-treatment (12 month), and post-treatment (18 month) assessments. Follow-up assessment procedures will take approximately 3-4 hours. The Research Coordinator will conduct a 15-minute Check-In at baseline to gather information about medications and services being received outside of this research study; the Supported Employment Specialists or Independent Assessors will conduct the 15-minute Check-In every 3 months after participants begin treatment groups (i.e., at 3-, 6-, 9-, 12-, 15-, and 18-months). The SE Specialists will also conduct the assessment of employment variables at these Check-Ins using the Workforce Participation form using an informal interview assisted by the use of a calendar and review of holidays and other activity anchors, supplemented by the ongoing assessment they conduct as part of the SE activities.

We are proposing a prospective randomized controlled trial with participants recruited from the CMCVAMC. We will randomize 96 patients (48 patients per condition). Independent assessors will be blinded to participant treatment group allocation. Assessment sessions will occur at baseline, and at 6, 12, and 18 months after therapy groups begin; brief check-ins will occur at each assessment session, and also at months 3, 9, and 15 after therapy groups begin.

Subjects in the iCBT condition will receive weekly or twice weekly group sessions for 12 months. iCBT follows a treatment manual developed by Perivoliotis, Grant, & Beck. The manual details the approach (engagement, behavioral activation, cognitive remediation/restructuring, maintenance) and individualized treatment planning. It also describes strategies and techniques to deal with positive and negative symptoms, mood symptoms, and suicidality. Included in these strategies are mindfulness exercises, designed to assist the participant in identifying feelings and biological processes that accompany a stimulus (i.e.,

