Supported Employment (SE). SE is the standard clinical intervention that is offered to Veterans with severe mental illness. Therefore, SE is not a research intervention. However, the supported employment specialists will be a part of the research team. Subjects randomized to either treatment group (i.e., iCBT, usual care) will participate in SE. All participants will also continue receive psychiatric care. Case management will continue for subjects already receiving such services. The SE program will adhere to the IPS model adopted by the CMCVAMC in 2005 as part of a national initiative (see Background, above). The IPS model has been well described¹⁸ and training occurs through a mentor-trainer model. Multiple studies have demonstrated the importance of high fidelity scores on SE program evaluation in terms of employment outcomes⁷⁷.

1.2. Explain if and how the follow-up of subjects will occur. The baseline assessment is designed to: a) determine baseline levels of work functioning, psychosocial functioning, symptomatology, cognitive impairment, and dysfunctional belief endorsement, and b) determine whether participants are eligible for the treatment phase of the study.

The research team will strive to form treatment groups as quickly as possible. However, it may take several weeks to accumulate enough eligible and willing participants to form a treatment group (i.e., 6-8 participants). The intention of the follow-up assessments and check-ins is to measure the impact of treatment on the study measures. Therefore, the follow-ups and check-ins are tied to the beginning of the treatment groups.

All participants who are eligible and consent to randomization will participate in three additional assessment sessions. The mid-treatment and post-treatment assessments are designed to measure change from baseline that occurred during the treatment period and will consist of a re-administration of the baseline measures. The follow-up assessment occurs 6 months after the end of the treatment period (18 months after treatment groups begin). The Research Coordinator will conduct the 15-minute check-in at baseline; the Supported Employment Specialists or Independent Assessors will conduct the check-in every 3 months after treatment groups begin (i.e., at 3-, 6-, 9-, 12-, 15-, and 18-months).

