This study is powered to detect a clinically significant difference between iCBT and the usual care conditions. Meta-analysis of medical and behavioral outcomes indicates that a medium effect-size between conditions will have a significant impact on quality of life. In a previous study we observed an average effect of about $d=0.55$ SD. To allow for a somewhat smaller effect in this proposed study, we design our study to have 80% power to detect clinically significant effect of $d=0.5$ SD. In the pilot data, we found a within-subject correlation structure consistent with a stationary autoregressive process with correlation parameter 0.4. We also assume a dropout rate of 20% for these power calculations. With these assumptions on effect size, covariance structure, and dropout rates, and with a two-sided alpha level of 0.05, the methods of Hedeker et al.⁸⁶ estimate that a sample size of 48 subjects per group will provide 80% power for the test of our primary hypothesis.

We believe that this is a conservative estimate, based on the larger effect size observed in our prior study, and the higher than expected dropout rate used in the calculation. In addition, our analyses will use the baseline measure of Psychosocial Functioning as a covariate, which should reduce the standard errors in our test, and therefore increase the smallest detectable effect size.

4.2. Define plans for data and statistical analysis, including key elements of the statistical plan, stopping rules and endpoints.

Planned Analyses

(i) Overview

Logistic, log-linear and linear random effects models (hierarchical regression models) will be implemented with random intercepts and slopes for longitudinal binary, count, and continuous outcomes, respectively. These models will contain separate main effects for change from baseline to each follow-up visit at 6, 12, and 18 months, main effect for the treatment, and interactions between the visit and treatment indicator variables. For each of the primary (workforce participation indices) and the secondary (Work Behavior Inventory, Specific Levels of Function) outcomes, separate intent-to-treat (ITT) tests and estimates (with 95% confidence intervals) of randomized group contrasts at 6, 12, and 18 months will be obtained from the estimates of the respective time-treatment interactions.

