While the present study is designed to minimize lost observations, the proposed random effects or hierarchical regression approach is superior to last observation carried forward in minimizing bias and Type 1 error and inferentially equivalent to multiple imputation.⁷⁹ To assess the sensitivity of treatment effect estimates to missing data, we will compare the results under the above hierarchical regression models with those based on shared parameter models that account for informative missingness that is dependent on unobserved outcomes through a latent variable.⁸⁰ If the results between the two approaches are similar then we will present the proposed hierarchical regression models as robust to informative missing data; otherwise we will note that the results may be

sensitive to informative missing data and augment them with those based on the shared parameter model.

(ii) **Work outcome.** The primary trial outcome measure, workforce participation (composite index) at 6, 12 and 18 months analyzed in the manner described above. A significant ITT difference on the total WBI score across 6 and 12 months would support the hypothesis that iCBT is more efficacious than usual care at improving work outcomes by the end of treatment (Primary Aim 1). Similarly, WBI score at 18 months is a secondary outcome, and a separate ITT effect on work outcomes at 18 months with the respective month-treatment interaction in favor of iCBT would support the hypothesis that it promotes better work outcomes than usual care during the 6 months after the completion of treatment (Secondary Aim 2).

(iii) **Functional outcome.** The second trial outcome measures include the Work Behavior Inventory and the total score on the Specific Levels of Functioning Inventory (SLOF) at 12 months A significant ITT difference on the WBI and the total SLOF score across 6, 12 months would support the hypothesis that ICBT is more efficacious than usual care at improving functioning by the end of treatment (Secondary Aim 1). Similarly, WBI and SLOF total score at 18 months is a secondary outcome, and the separate ITT effects on functioning at 18 months with the respective month-treatment interaction in favor of iCBT would support the hypothesis that it promotes better functioning than usual care during the 6 months after the completion of treatment (Secondary Aim 3).

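### The primary work outcome has no single time window, and the plan does not say how the 3-monthly work forms become 6-, 12- and 18-month values

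*Combined protocol and SAP*

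**What the plan says.** All references are to the Combined protocol and SAP.

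- **Section K** states the primary aim as to "improve work outcomes at post-treatment to a greater extent than usual care". The outcome that follows is "several work-related indices of work participation across the 18 months of active study involvement".
- **Section M.3.2** describes reassessment "producing mid-treatment (6 month) end-of-treatment (12 month), and post-treatment (18 month) assessments", and O.1.1 repeats this. There, post-treatment is month 18.
- **Section O.1.2** says the "mid-treatment and post-treatment assessments are designed to measure change from baseline that occurred during the treatment period", and describes the month-18 visit separately as the follow-up. There, post-treatment is the end of the 12-month treatment period.
- **Section W.4.2 (i)** specifies a model with "separate main effects for change from baseline to each follow-up visit at 6, 12, and 18 months" and takes a treatment contrast at each of those visits. It applies this to every workforce index as well as to the WBI and the functioning scale.
- **Section W.4.2 (ii)** takes "workforce participation (composite index) at 6, 12 and 18 months analyzed in the manner described above". The next sentence judges Primary Aim 1 on the WBI over 6 and 12 months, at the close of treatment. A further sentence, also about the WBI, reads an 18-month effect as showing that iCBT "promotes better work outcomes than usual care during the 6 months after the completion of treatment (Secondary Aim 2").
- **Section O.1.1 and Table 1 (O.1.3)** schedule the Workforce Participation form at baseline and at 3, 6, 9, 12, 15 and 18 months. O.2.2 mentions a reporting period but does not define it.
- **Section W.4.1** names the composite as the primary outcome variable and justifies 48 per group without saying which contrast is powered.

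**The concern.** For an outcome that accumulates over time, such as weeks worked, the window is part of the definition of the endpoint. The text supports at least four windows: one post-treatment visit (month 12 or 18, depending on the section), the whole 18 months, three separate visit contrasts, and months 6 and 12 together. None is named as decisive, and alpha is left uncorrected at 0.05. The window that determines success could therefore be settled once results are known.

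A second gap sits underneath. Six follow-up forms are collected, but the model has terms for only three time points. Nothing says how far back a form reaches, what happens to the forms at 3, 9 and 15 months, or whether total weeks worked restarts at each interval or accumulates. The same data could thus give different visit values and a different meaning to the 18-month contrast.

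**Working it through.** **1. Reproducing the planned sample size.** Inputs from W.4.1: d = 0.5, autoregressive correlation 0.4, 20% dropout, two-sided alpha 0.05, 80% power, 48 per group. I take the correlation as applying per 6-month visit and d on the SD of one visit value.

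For a weighted mean of visits with variance v (in units of the visit variance), n per group = 2(1.960 + 0.842)² v / d² = 2 × 7.849 × v / 0.25. Power at 48 per group is Φ(√(48 × 0.25 / 2v) − 1.960). Dropout enters by dividing each visit's variance by its retention r.

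For the mean of months 6 and 12, v = ¼(1/r₆ + 1/r₁₂ + 2 × 0.4/√(r₆r₁₂)).

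| Contrast | Retention | v | n for 80% | Power at 48 |
|---|---|---|---|---|
| Mean of 6 and 12 | 100%, 90% | 0.739 | 47 | 81.3% |
| Mean of 6 and 12 | 93.3%, 86.7% | 0.779 | 49 | 79.3% |
| Mean of 6 and 12 | 100%, 80% | 0.786 | 50 | 78.9% |
| Mean of 6 and 12 | 90%, 80% | 0.826 | 52 | 76.9% |
| Mean of 6 and 12 | 80%, 80% | 0.875 | 55 | 74.5% |
| Mean of 6, 12 and 18 | 100%, 90%, 80% | 0.612 | 39 | 87.9% |
| Mean of 6, 12 and 18 | 80% throughout | 0.683 | 43 | 84.2% |
| One visit | 100% | 1.000 | 63 | 68.8% |
| One visit | 80% | 1.250 | 79 | 59.1% |

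The stated 48 is recovered, within rounding, for the mean of months 6 and 12 under the first three dropout patterns. It is not recovered for a single visit or for the mean of all three.

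**2. Coverage if each form looks back 3 months (assumption).** If only the 6-, 12- and 18-month forms are used, months 0–3, 6–9 and 12–15 are never counted: 3 × 13 = 39 of 78 weeks.

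**3. Content of the month-18 value if indices are cumulative (assumption).** Treatment lasts 12 months, so 12 of the 18 months in that value (67%) are on treatment.

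**4. Six-month intervals from paired forms.** The forms at 3 and 6, 9 and 12, and 15 and 18 months cover all 18 months. No on-treatment time falls in the last interval.

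**5. Illustration only.** I simulated weekly job finding (0.02–0.04) and job loss (0.02–0.10, so jobs averaging 10–50 weeks). These rates are assumed; the documents give none.

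- Under step 2, about 45–47% of worked weeks are lost. Of people who worked in months 0–6, about 5–21% would be scored as not working at month 6.
- The months 0–12 treatment effect hardly moves. For control finding rate 0.02 against 0.03, 0.035 and 0.04 (loss 0.05, 0.05 and 0.10), d with all weeks against d with the 6- and 12-month forms only is 0.30 vs 0.29, 0.44 vs 0.42, and 0.57 vs 0.52.
- Under step 3, with a job-finding effect that stops at month 12, those three cases give a cumulative 18-month d of 0.29–0.51. Work done in months 12–18 shows 0.11–0.16. With 50-week jobs and finding rate 0.04, the figures are 0.54 and 0.28.

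**The case against.** A reader might infer that the planned analysis must either drop half the work record or credit on-treatment work to the post-treatment period. The documents do not support that. Each outcome needs a look-back rule they do not contain, and six-month intervals built from paired forms would avoid both. Nothing rules such intervals out, and the data would allow them: O.1.1 describes a calendar-aided interview supplemented by continuing supported-employment records, and O.2.1.1 has the form record when jobs were obtained.

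A reader might also infer that Secondary Aim 2 would succeed on work done before month 12. As worded, it concerns the WBI. O.2.1.1 scores that measure at a point in time, with 0 when the person is not working, so it cannot carry earlier work forward. The risk reaches the workforce indices only through the general 18-month contrast in W.4.2 (i).

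Nor does losing half the weeks imply a badly distorted treatment effect; the illustration shows little change over months 0–12. Finally, an 18-month window is a legitimate choice. The success statement pointing to 6 and 12 months is about the WBI, so it does not settle the matter for the composite.

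All of this stands. It limits the claimed consequences, but it does not supply the missing window or derivation rule.

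**Conclusion.** The conflict between sections is established from the text alone, and so is the absence of a look-back or accumulation rule. As written, the primary test cannot be identified.

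The consequences are conditional: up to 39 of 78 weeks omitted if recall is 3 months and only three forms are used, or 12 on-treatment months inside the 18-month value if indices accumulate. The choice of contrast also matters for power: about 79–81% for the mean of months 6 and 12 with gradual dropout, 84–88% for the mean of all three visits with 20% dropout, and 59–69% for a single visit.

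The power figures assume that d = 0.5 and correlation 0.4 apply to the composite; the plan does not show that the pilot correlation came from that outcome. The simulated effects are illustrative and are not evidence of severity. The point needs correcting before analysis because the deciding window could otherwise be picked after the results are seen.

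**What to change.** 1. Define the reporting period of the Workforce Participation form. Derive every work index over non-overlapping months 0–6, 6–12 and 12–18 from the consecutive 3-monthly forms, including those at 3, 9 and 15 months.
2. Name one primary window and one contrast for the composite. Either months 0–12 (matching the end-of-treatment aim) or all 18 months (matching Section K) is defensible; the sponsor should choose before seeing outcome data.
3. Restate Primary Aim 1 in terms of the composite, not the WBI. Give post-treatment one meaning, and make K, M.3.2, O.1.1, O.1.2 and W.4.2 agree.
4. Base any post-treatment claim about the work indices only on work done in months 12–18.
5. Restate power in W.4.1 for the chosen contrast and its dropout pattern.

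The cost is wording, a simple derivation and a revised power statement; no new data are collected. The small downside is that a months 12–18 contrast is likely to look less favourable than a cumulative 18-month total.
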